15.6 Contrast Sensitivity

Contrast sensitivity testing will be performed once at the screening visit, twice at the baseline visit, and once at 3, 6, 9, and 12 months after study agent administration, and at each long-term follow-up visit. Contrast sensitivity will be measured using Pelli-Robson charts.

The observed and change from baseline (average of the two baseline results) log contrast sensitivity for each eye and both eyes will be summarized using continuous descriptive statistics by visit for each group and for all subjects. The paired t-tests and figures as specified in Section 15.1 will be created. A subject listing of contrast sensitivity testing results will also be produced.

15.7 Full-field and Multi-Focal Electroretinography

Electroretinography testing of both eyes will be performed at the screening and baseline visits and at 3, 6 and 12 months after study agent administration, using both ffERG and mfERG procedures.

If there is a significant change in the ERG at the 12-month visit compared to the ERG at the screening and baseline visits, the ERG will be repeated at the long-term follow-up visits.

The observed and change from baseline full-field and multi-focal ERG results will be summarized separately for each eye using continuous descriptive statistics by visit for each group and for all subjects. The paired t-tests and figures as specified in Section 15.1 will be created. Continuous parameters for full-field ERG include: Max B-wave (amplitude), Max A-wave (amplitude), Ratio of A-wave to B-wave (amplitudes), Dark-adapted response for B-wave alone at 0.01 flash (represents a pure B wave), Dark-adapted response for A-wave alone at 10 flash, Light-adapted 30 hz peak-to-peak amplitude. An additional assessment of ffERG responses will be performed using the method of Hood and Birch¹. The amplitude of the leading edge of the a-wave will be determined from a set of three additional white flashes of 25, 50 and 100 cd/m2 presented under dark adapted responses. The rod b-wave component will then be isolated by subtracting the rod a-wave from the ERGs to each of the three flash intensities. Continuous parameters for multi-focal parameters include: Latency Ring 1 (ms), Latency Ring 2 (ms), Latency Ring 4 (ms), Latency Ring 5 (ms), Latency Ring 6 (ms), Amplitude Ring 1

08 August 2017

(nV/deg2), Amplitude Ring 2 (nV/deg2), Amplitude Ring 3 (nV/deg2), Amplitude Ring 4 (nV/deg2), Amplitude Ring 5 (nV/deg2), Amplitude Ring 6 (nV/deg2) and sum of amplitude of all rings. Subject listings of full-field and mfERG results will also be produced.

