Individuals who have participated in the natural history study XLRS-001, entitled "Clinical Evaluation of Individuals with XLRS", may have discontinued their participation in that study and enrolled in this study if all appropriate entry criteria were met. In this case, results of the evaluations from the most recent visit in the natural history study could be used as part of the appropriate screening visit evaluations for this study, as long as all the evaluations were conducted according to the Study Manual of Procedures and Reading Center Manual of Procedures of this study, and the visit occurred no more than 3 months prior to the planned date of study agent administration. If the most recent visit examinations are performed.

Enrollment began with Group 1A and will proceed to subsequent groups after review of safety data by a Data and Safety Monitoring Committee (DSMC). After review of safety data from Group 1A, participants will be enrolled in Groups 1B and 2 concurrently. After review of safety data from Groups 1A, 1B and 2, participants will be enrolled in Group 3. After review of safety data from Groups 1A, 1B, 2, and 3, participants \geq 18 years of age will be enrolled in Group 4. As ocular inflammation has been seen in the first 12 subjects enrolled in the study and pediatric participants might be more prone to inflammation, pediatric participants (age 6-17) in this study will first be treated at the middle dose (Group 2A) prior to the enrollment in Group 4.

Within groups 1A, 2, 2A and 3, enrollment of participants will be staggered by at least 2 weeks to allow adequate time for review of safety information by the investigators and sponsor.

Within group 4, enrollment of the first 3 pediatric participants will be staggered by at least 2 weeks to allow adequate time for review of safety information by the investigators and sponsor.

Approximately 27 participants are to be enrolled in this study. Enrollment in this study is anticipated to take approximately 30 months. Enrolled participants will have frequent follow-up visits during the first year after study agent administration.

To monitor for delayed AEs and assess the duration of any changes in visual function or structure that occur, participants are followed annually for an additional 4 years after the Month 12 visit.

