¹ Ophthalmic examinations include slit lamp examination, tonometry, indirect ophthalmoscopy and retinal biomicroscopy in both eyes will be evaluated at each visit, except on Day 0 (Visit 3) when the only required exam is tonometry of the study eye about 30 minutes after study agent administration is completed.

¹ ERG testing at LTFU visit if a significant change seen in ERG at month 12 visit compared to screening and baseline visits.

5. Study Treatment

All subjects will receive rAAV2tYF-CB-hRS1, a replication-incompetent, recombinant adeno-associated virus (rAAV) vector that expresses the RS1 protein after the vector enters retinal cells. The dose level of each group is described in the schematic of study design shown in section 4.1.

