9.2 Missing or Inconclusive Data Handling

Missing data will be treated as missing and no imputation will be performed unless otherwise specified.

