9.4 Data Analysis Conventions

All data analysis outlined in this SAP will be performed by Statistics & Data Corporation (SDC). Statistical programming and analyses will be performed using SAS[®] Version 9.4 or higher. Output will be provided in Rich Text Format (RTF) for tables and figures and Portable Document Format (PDF) for tables and listings using landscape orientation. All study data for treated subjects will be listed by group, subject, and visit (as applicable) unless otherwise specified. Only a disposition listing will be created for screen failed subjects.

Summaries for continuous and ordinal variables will include the number of observations (n), arithmetic mean, standard deviation (SD), median, minimum, and maximum. Minima and maxima will be reported with the same precision as the raw values; means and medians will be presented to one additional decimal place than reported in the raw values. Standard deviations will be presented to two additional decimal places than reported in the raw values. Summaries for discrete variables will include frequency counts and percentages. All percentages will be rounded to one decimal place (i.e., XX.X%). Change from baseline will be calculated as follow-up visit values minus the baseline value.

All statistical tests will be two-sided with alpha level of 0.05. Unless otherwise specified, summaries will be presented by group (1A, 1B, 2, 2A, 2+2A, 3, 4, 3+4, and all subjects) and, where appropriate, visit.

Unscheduled visits will not be summarized. Study visits will be referred to in all tables and listings with the expected study day/month/year corresponding to the visit to enable reviewers to understand the assessment timing without referring to the protocol visit schedule. The following table shows the scheduled study visits, their planned study day:

Scheduled Visit	Planned Study Day
Visit 1	Screening
Visit 2	Baseline
Visit 3	Day 0
Visit 4	Day 1
Visit 5	Day 7
Visit 6	Day 14
Visit 7	Month 1
Visit 8	Month 2
Visit 9	Month 3
Visit 10	Month 6
Visit 11	Month 9
Visit 12	Month 12
Visit 13	Year 2
Visit 14	Year 3
Visit 15	Year 4
Visit 16	Year 5
1	

10. Disposition of Subjects

The following disposition items will be summarized:

- The number of subjects screened (who signed the informed consent/assent form)
- The number of screen failures
- The number of subjects enrolled (who met the enrollment criteria)
- The number of subjects treated (who received an intravitreal injection of study agent)

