15.1 Visual Acuity

BCVA testing will be performed once at the screening visit, twice at the baseline visit, and once at each visit after study agent administration, including each long-term follow-up visit. BCVA will be determined using a standard ETDRS visual acuity testing protocol.

The observed and change and percent change from baseline (average of the two baseline results) visual acuity will be summarized for each eye using continuous descriptive statistics by visit for each group and for all subjects. P-values from paired t-tests comparing post-baseline visits with baseline visit and p-values from 2-sample t-tests comparing study eye with fellow eye will be presented for Treatment Groups 2A, 2+2A, 4, 3+4, and all subjects combined. All inferential statistics are

exploratory in nature. Visual acuity data will be presented as the letter score and the logMAR (calculated as (85-ETDRS)/50, where ETDRS is the ETDRS/EVA letter score) at each time point. Change from baseline in ETDRS letter score will be summarized for the following categories: <=-15, -15 to <-8, -8 to <0, no change, >0 to 8, >=8 to 15, >=15. A subject listing of visual acuity will also be produced.

Box plots of change from baseline in ETDRS BCVA by visit will be presented by group and overall (one box for each group side-by-side at each visit) and repeated by eye (study eye and fellow eye).

Line plots of ETDRS BCVA letter score by visit with 95% confidence intervals (CIs) will be plotted by group and overall. Right and left eyes will be displayed side-by-side on the same page.

Histograms of ETDRS BCVA score at each visit by group and overall will be presented in panel graphs (one panel for each group by visit) and repeated by eye (study eye and fellow eye).

08 August 2017

Scatter plots of ETDRS BCVA score at follow-up visits versus baseline (also known as shift plots) by group and overall will be presented in panel graphs (one panel for each group by visit) and repeated by eye (study eye and fellow eye). A regression line and a line going through the origin will be overlaid in the scatter plots.

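### SAP 15.7 would summarise and t-test long-term ERG in participants retested because of their Month 12 ERG; since protocol Version 8.0 this affects only recordings made at Year 2 or later before that amendment

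*SAP*

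**What the plan says.** SAP 15.7 schedules ERG at screening, baseline and Months 3, 6 and 12. Long-term ERG is conditional: "If there is a significant change in the ERG at the 12-month visit compared to the ERG at the screening and baseline visits", the test is repeated at the long-term visits. The ERG footnote to the schedule in SAP 4.2 says the same: "ERG testing at LTFU visit if a significant change seen in ERG at month 12 visit compared to screening and baseline visits". Neither place gives a threshold, a direction, a parameter or an eye. Neither says outright that the rule applies participant by participant, although that is the natural reading.

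SAP 15.7 then directs that, eye by eye, ERG results be summarised "using continuous descriptive statistics by visit for each group and for all subjects. The paired t-tests and figures as specified in Section 15.1 will be" produced. The tests it borrows from SAP 15.1 are "P-values from paired t-tests comparing post-baseline visits with baseline visit", presented for Groups 2A, 2+2A, 4, 3+4 and all subjects combined. SAP 9.4 lists Years 2 to 5 as scheduled Visits 13 to 16, so its exclusion of unscheduled visits does not remove them. On participants without a recording, SAP 9.2 says: "Missing data will be treated as missing and no imputation will be performed" unless otherwise specified.

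The current protocol differs. Protocol 6.11 ends ERG at Month 12. Protocol 6.15 lists clinical evaluation, visual acuity and ophthalmic examinations as the long-term testing. Appendix A has no ERG mark at Years 2 to 5. The change log dates the removal of long-term efficacy testing to Version 8.0, 21 October 2019. SAP 1 states that the SAP serves Version 6.0 and that its statistical methods take precedence over those in the protocol.

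**The concern.** In the SAP, OCT, perimetry, microperimetry, reading speed and contrast sensitivity are due at every long-term visit without condition. ERG alone is conditional on its own earlier result, yet it receives the same by-visit means, paired tests and figures. A Year 2 ERG row would carry the label of a group, or of all subjects, while holding only those whose Month 12 ERG had moved.

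The comparison is also not independent of the selection. The SAP 4.2 schedule marks ERG once at baseline, where the tests just named are marked twice. Under SAP 9.3 that single value is the analysis baseline, and it also enters the trigger. A participant whose baseline ERG read low by chance is more likely to be retested for apparent improvement, and is then compared with the same low value at Year 2. Protocol 3 gives the duration of any visual change as one purpose of long-term follow-up, and that is the question such a row would seem to answer.

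**Working it through.** **Plan's own figures.** None is given for ERG. The only power-type figures, in Protocol 10.5 and SAP 6, are exact upper limits for the DLT rate. They reproduce, 1 − 0.025^(1/9) = 33.63% and 1 − 0.025^(1/27) = 12.77%, but do not bear on this point.

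**Which recordings can be affected.** The change log dates the original protocol 6 March 2015 and Version 8.0 21 October 2019.
- Year 5: March 2015 + 5 years = March 2020, after Version 8.0. Not reachable by the amendment date.
- Year 4: needs dosing by about October 2015. Year 3: by about October 2016. Year 2: by about October 2017.
- SAP 4.1, in a document dated 8 August 2017, reports that "ocular inflammation has been seen in the first 12 subjects enrolled in the study". Those 12 had therefore been treated by then, and their Year 2 visits fell due by about August 2019, before the amendment.

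So some Year 2 visits, and possibly some Year 3 or 4 visits, came while the conditional rule could apply. Whether any ERG was triggered is not stated.

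**Persistence of chance change.** The documents give no ERG variability and no threshold. Assumed: no treatment effect, and independent errors of SD 1 (one retest SD) at screening (S), baseline (B), Month 12 (M) and Year 2 (Y).
- Selection contrast: D = M − (S + B)/2. Variance = 1 + 1/4 + 1/4 = 1.5, SD = 1.225.
- Year 2 change in the table: Y − B. Its covariance with D comes only through B: (−1/2) × (−1) = 0.5.
- Share of the selected change that persists: 0.5/1.5 = 1/3. The Month 12 error itself does not carry over.

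If only improvement beyond c SDs of D triggers a retest, mean D among those selected is 1.225 × φ(c)/(1 − Φ(c)):

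| c | Share selected | φ/(1 − Φ) | Mean Month 12 change | Mean Year 2 change |
|---|---|---|---|---|
| 1.0 | 15.9% | 1.525 | 1.87 | 0.62 |
| 1.5 | 6.7% | 1.939 | 2.37 | 0.79 |
| 1.96 | 2.5% | 2.338 | 2.86 | 0.95 |

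If selection were against the baseline visit alone, the variance is 2, the covariance 1 and the persisting share 1/2. At c = 1 that is 2.16 at Month 12 and 1.08 at Year 2.

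**Effect on the t-test.** These are simulated rates for 27 participants with no effect, over cut-offs from 0.5 to 1.96 SD, counting trials with at least two retested. SAP 9.4 sets the standard: "All statistical tests will be two-sided with alpha level of 0.05".

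| Who is retested | Rejection rate |
|---|---|
| Everyone | 5.0% |
| Improvers, against mean of screening and baseline | 8.5% to 14% |
| Improvers, against baseline alone | 15% to 35% |
| Change in either direction | 4.7% to 6.5%, mean Year 2 change about zero |

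**How many would be retested by chance.** Among the 12 subjects, the one-parameter, one-direction shares above give 12 × 0.025 = 0.3 to 12 × 0.159 = 1.9. At the other extreme, suppose a 5% change in any of the 18 ERG parameters named in SAP 15.7 (6 full-field, 12 multifocal) counted, and the parameters were independent. Then 1 − 0.95^18 = 60% would qualify, or about 7 of 12. ERG parameters are unlikely to be independent, so that is an upper extreme.

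**The case against.** The strongest reply is that the rule is obsolete. Under Version 8.0 no ERG is done after Month 12, and the documents do not show that any long-term ERG was ever triggered. This stands, and it limits the point to a possible remnant of earlier recordings. It does not withdraw the analysis instruction, because the SAP was not brought into line and says that its methods prevail.

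Second, the SAP gives no direction. With two-directional selection the mean Year 2 change is about zero and the test keeps roughly its nominal level. This also stands. What remains is that the row is labelled as a group it does not represent, and that each retested participant's apparent persistence is still partly an artefact of the shared baseline.

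Third, SAP 15.1 calls its inferential statistics exploratory, SAP 9.4 requires n in every continuous summary, and SAP 15.7 already provides subject listings. A row based on one or two people would be visible as such, and with fewer than two there is no t-test. This limits the harm, although neither n nor an exploratory label tells the reader that the participants were chosen on their Month 12 ERG.

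A reader might infer more: that ERG is still being collected through Year 5, and that the tables will show a false lasting benefit. The documents support neither. Collection ended with Version 8.0. A one-way bias needs a one-way trigger, which the SAP does not state. The Version 8.0 log entry also reports no evidence of a treatment effect at 12 months, which makes a reading of durable benefit less likely.

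**Conclusion.** The point holds as a minor one. SAP 15.7 directs group-level summaries and paired t-tests for ERG visits that, under its own rule, include only participants with a Month 12 change, and it neither excludes nor labels them. This matters only for ERGs recorded at Year 2 or later before Version 8.0, a number that the documents do not give and that is probably very small.

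For those rows the labelling fault is certain, given the per-participant reading. Bias in the mean is conditional: 0.62 to 0.95 retest SDs if selection was mainly in one direction at cut-offs of 1 to 1.96 SD, and about zero if both directions qualified. These sizes rest on no treatment effect, equal independent errors and selection against the mean of screening and baseline. None of these can be checked from the documents.

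**What to change.** Align SAP 4.2 and 15.7 with the current protocol:
- Remove the Year 2 to 5 ERG mark and its footnote from the SAP 4.2 schedule, and the conditional repeat from SAP 15.7.
- Limit ERG group summaries, paired t-tests and figures to Months 3, 6 and 12.
- Show any ERG recorded at Year 2 or later only in the by-subject listing, next to that participant's screening, baseline and Month 12 values, marked as obtained because of the Month 12 result.
- State beside that listing what was taken as a significant change, so that a reader can see how participants came to be retested.

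The cost is SAP wording and fewer table rows. The downside is that there is no group-level ERG summary after Month 12, which data selected in this way could not support.

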15.8 Quality of Life Analyses

15.8.1 25-Question Visual Function Questionnaire (VFQ-25)

For participants \geq 16 years of age, the 25-question visual function questionnaire (VFQ-25) overall composite score and the following sub-scale scores will be calculated based on the VFQ-25 Manual.

Item Numbers Original Response Category Score for Analysis 1,3,4,15c^(a) 5,6,7,8,9,10,11,12,13,14,16,16a * 17,18,19,20,21,22,23,24,25 Item 15c has four-response levels, but is expanded to a five-levels using item 15b. (a) Note: If 15b=1, then 15c should be recoded to "0" If 15b=2, then 15c should be recoded to missing. If 15b=3, then 15c should be recoded to missing.

The VFQ-25 is scored according to the following table:

* Response choice "6" indicates that the person does not perform the activity because of non-vision related problems. If this choice is selected, the item is coded as "missing."

Next create the VFQ-25 Sub-scales by averaging non-missing assigned scores as indicated in the following table:

Sub-scale	Number of Items	Items to be averaged (after recoding)
General Health	1	1
General Vision	1	2
Ocular Pain	2	4, 19

Near Activities	3	5, 6, 7
Distance Activities	3	8, 9, 14
Vision Specific:		
Social Functioning	2	11, 13
Mental Health	4	3, 21, 22, 25
Role Difficulties	2	17, 18
Dependency	3	20, 23, 24
Driving	3	15c, 16, 16a
Color Vision	1	12
Peripheral Vision	1	10

The mean of the sub-scale items is the sub-scale score. The VFQ-25 composite score is the mean of the sub-scale scores.

Descriptive statistics for the scores will be used to summarize the overall composite score and sub-scale scores at each study visit. The change in the overall composite score and sub-scale scores from the baseline visit to each follow-up visit will also be summarized. The paired t-tests as specified in Section 15.1 will be created.

Two listings will be prepared. One listing displaying the sub-scales and composite score at each visit will be produced. The second listing will display the original response categories for each item at each visit for each patient.

15.8.2 Functional Vision Questionnaire for Children and Young People (FVQ_CYP)

For participants < 16 years of age, the Functional Vision Questionnaire for Children and Young People (FVQ_CYP) summary score and the sub-scale scores will be calculated based on the FVQ_CYP manual.

The FVQ_CYP (36) summary score will be calculated by converting the response categories 1-4 to 0-3 scores and adding the scores on the 36 items. A higher summary score denotes a higher level of functional difficulty. A pro-rated summary score will not be calculated for a respondent who omitted answers to more than 20% of the questionnaire items (8 out of 36 items).

Descriptive statistics for the score will be used to summarize the summary score at each study visit. The change in the summary score and sub-scale scores from the baseline visit to each follow-up visit will also be summarized. The same inferential statistics as specified in Section 15.1 will be created.

A listing displaying the summary score and original response categories at each visit will be produced.

15.9 Fundus Photography

Fundus photography will be performed at the baseline visit and at the visit 12 months after study agent administration.

The results will be summarized using counts and percentages for each group and for all subjects at each visit for each eye. Percentages will be based on the number of subjects with responses. Fundus

08 August 2017

photography parameters include Any evidence of increased inflammation, Hemorrhage, Retinal detachment, Is there RPE disturbance or atrophy in the fovea, Any changes from baseline visit. A subject listing of the fundus photograph parameters will also be produced.

16. Long-term Follow-Up (LTFU)

After the completion of 9 study visits over the course of one year after study agent administration, longterm follow-up (LTFU) will be conducted annually for an additional 4 years after the Month 12 visit. In accordance with regulatory guidance for gene therapy clinical trials, information will be obtained about any cancer, neurological, autoimmune or hematological disorder that developed or worsened since the last visit. A subject listing containing this information will be provided.

17. Interim Analysis

No interim analysis will be conducted for this study. Preliminary analyses of available data may be conducted during the study.

18. Data and Safety Monitoring Committee

Refer to section 4.1.

19. Changes from Protocol-Stated Analyses

- Change over time in titers of serum antibodies and IFN-γ ELISPOT responses to retinoschisin (RS1) is moved from secondary safety outcomes to other outcomes.
- Inferential statistics for all efficacy endpoints will be calculated.
- Visual field parameter (square root of the loss variance) will not be read by the Reading Center.

20. References

¹ Hood DC and Birch DB. A computational model of the amplitude and implicit time of the b-wave of the human ERG. Vis Neurosci 1992;8:107-26

² Patel PJ, Chen FK, Da Cruz L, Rubin GS, and Tufail A. *Test-retest variability of reading performance metrics using MNREAD in patients with age-related macular degeneration*. Invest Ophthalmol Vis Sci 2011;52:3854-9

21. Revision History

Documentation of revision to the SAP will commence after approval of the Final version 1.0.

22. Tables

Table Number	Title
Table 14.1.1	Subject Disposition
Table 14.1.2	Demographics

Table 14.1.3	Vital Signs
Table 14.1.4	Medical History
Table 14.1.5	Concomitant Medications
Table 14.2.1.1	Best Corrected Visual Acuity
Table 14.2.1.2	Best Corrected Visual Acuity – Inferential Statistics
Table 14.2.1.3	Best Corrected Visual Acuity Letter Score - Categorical Summary
Table 14.2.2.1	Spectral Domain Optical Coherence Tomography
Table 14.2.2.2	Spectral Domain Optical Coherence Tomography – Inferential Statistics
Table 14.2.3.1.1	Static Perimetry
Table 14.2.3.1.2	Static Perimetry – Inferential Statistics
Table 14.2.3.2.1	Kinetic Perimetry
Table 14.2.3.2.2	Kinetic Perimetry – Inferential Statistics
Table 14.2.4.1	Microperimetry
Table 14.2.4.2	Microperimetry – Inferential Statistics
Table 14.2.5.1	Reading Speed
Table 14.2.5.2	Reading Speed – Inferential Statistics
Table 14.2.6.1	Contrast Sensitivity
Table 14.2.6.2	Contrast Sensitivity – Inferential Statistics
Table 14.2.7.1.1	Full-field Electroretinography
Table 14.2.7.1.2	Full-field Electroretinography – Inferential Statistics
Table 14.2.7.2.1	Multi-focal Electroretinography

Table 14.2.7.2.2	Multi-focal Electroretinography – Inferential Statistics
Table 14.2.8.1	25-Question Visual Function Questionnaire (VFQ-25)
Table 14.2.8.2	25-Question Visual Function Questionnaire (VFQ-25) – Inferential Statistics
Table 14.2.8.3	Functional Vision Questionnaire for Children and Young People (FVQ_CYP)
Table 14.2.8.4	Functional Vision Questionnaire for Children and Young People (FVQ_CYP) – Inferential Statistics
Table 14.2.9	Fundus Photography
Table 14.3.1	Overall Summary of Treatment-Emergent Adverse Events
Table 14.3.2	Ocular Treatment-Emergent Adverse Events by System Organ Class and Preferred Term
Table 14.3.3	Non-Ocular Treatment-Emergent Adverse Events by System Organ Class and Preferred Term
Table 14.3.4	Grade 3 or 4 Treatment-Emergent Adverse Events that Occurred During the 12 Months after Study Drug Administration by System Organ Class and preferred Term
Table 14.3.5	Ocular Treatment-Emergent Adverse Events Related to Study Agent by System Organ Class and Preferred Term
Table 14.3.6	Non-Ocular Treatment-Emergent Adverse Events Related to Study Agent by System Organ Class and Preferred Term
Table 14.3.7	Ocular Treatment-Emergent Adverse Events Related to Injection by System Organ Class and Preferred Term
Table 14.3.8	Non-Ocular Treatment-Emergent Adverse Events Related to Injection by System Organ Class and Preferred Term
Table 14.3.9	Serious Adverse Events by System Organ Class and Preferred Term

Table 14.3.10	Serious Adverse Events Related to Study Agent by System Organ Class and Preferred Term
Table 14.3.11	Serious Adverse Events Related to Injection by System Organ Class and Preferred Term
Table 14.3.12	Ocular Treatment-Emergent Adverse Events by System Organ Class, Preferred Term, and Maximum Intensity
Table 14.3.13	Non-Ocular Treatment-Emergent Adverse Events by System Organ Class, Preferred Term, and Maximum Intensity
Table 14.4.1.1	Hematology Results by Group and Visit
Table 14.4.1.2	Hematology Shifts from Baseline
Table 14.4.2.1	Chemistry Results by Group and Visit
Table 14.4.2.2	Chemistry Shifts from Baseline
Table 14.4.3	Coagulation Results by Group
Table 14.4.4	Immunology Results by Group and Visit
Table 14.4.5	Slit Lamp Examination – Shift Table
Table 14.4.6	Tonometry
Table 14.4.7	Indirect Ophthalmoscopy – Shift Table

23. Listings

Listing Number	Title
Listing 16.2.1.1	Subject Disposition –Treated Subjects
Listing 16.2.1.2	Subject Disposition – Screen Failed Subjects
Listing 16.2.2	Protocol Deviations
Listing 16.2.3	Inclusion/Exclusion Criteria Violations

08 August 2017

Listing Number	Title
Listing 16.2.4.1	Demographics
Listing 16.2.4.2.1	Physical Examination Abnormalities at Baseline
Listing 16.2.4.2.2	Physical Examination Abnormalities occurring During the Study
Listing 16.2.4.3	Vital Signs
Listing 16.2.4.4	Medical History
Listing 16.2.4.5.1	Concomitant Medications
Listing 16.2.4.5.2	Carbonic Anhydrase Inhibitor Use
Listing 16.2.5	Study Agent Administration
Listing 16.2.6.1	Best-corrected Visual Acuity
Listing 16.2.6.2	Spectral Domain Optical Coherence Tomography
Listing 16.2.6.3	Static Perimetry
Listing 16.2.6.4	Kinetic Perimetry
Listing 16.2.6.5	Microperimetry
Listing 16.2.6.6.1	Reading Speed (Part 1)
Listing 16.2.6.6.2	Reading Speed (Part 2)
Listing 16.2.6.7	Contrast Sensitivity
Listing 16.2.6.8	Full-field Electroretinography
Listing 16.2.6.9	Multi-focal Electroretinography
Listing 16.2.6.10.1	25-Question Visual Function Questionnaire (VFQ-25) – Overall and SuB-Scale Scores

Listing Number	Title
Listing 16.2.6.10.2	25-Question Visual Function Questionnaire (VFQ-25) – Categorical Responses
Listing 16.2.6.10.3	Functional Vision Questionnaire for Children and Young People (FVQ_CYP)
Listing 16.2.6.11	Fundus Photography
Listing 16.2.7.1	Adverse Events by System Organ Class and Preferred Term
Listing 16.2.7.2	Serious Adverse Events
Listing 16.2.7.3	Adverse Events Leading to Early Termination
Listing 16.2.7.4	Adverse Events of Dose Limiting Toxicity (DLT)
Listing 16.2.8.1	Hematology Results
Listing 16.2.8.2	Chemistry Results
Listing 16.2.8.3	Coagulation Results
Listing 16.2.9	Immunology Result
Listing 16.2.10	Vector Analysis Results
Listing 16.2.11	Slit Lamp Examination
Listing 16.2.12	Tonometry
Listing 16.2.13	Indirect Ophthalmoscopy
Listing 16.2.14	Long-Term Follow-Up Information
Listing 16.2.15	Investigator Comments

24. Figures

Figure Number	Title
Best-corrected Visual Acuity Score	
Figure 14.2.1.1.1	Box Plot of Change from Baseline in ETDRS Best-corrected Visual Acuity Score – Study Eye
Figure 14.2.1.1.2	Box Plot of Change from Baseline in ETDRS Best-corrected Visual Acuity Score – Fellow Eye
Figure 14.2.1.2.1	Histograms of ETDRS Best-corrected Visual Acuity Score – Study Eye
Figure 14.2.1.2.2	Histograms of ETDRS Best-corrected Visual Acuity Score – Fellow Eye
Figure 14.2.1.3.1	Shift Plots of ETDRS Best-corrected Visual Acuity Score – Study Eye
Figure 14.2.1.3.2	Shift Plots of ETDRS Best-corrected Visual Acuity Score – Fellow Eye
Figure 14.2.1.4	Line Plots of ETDRS Best-corrected Visual Acuity Score
Static Perimetry: 3	0 degree Hill of Vision (decibel steradians), Volume of full field Hill of
Vision (decibel ste	radians), Total Volume Loss (decibel steradians), Reliability Factor
Figure 14.2.2.1.1	Box Plot of Change from Baseline in Static Perimetry – Study Eye
Figure 14.2.2.1.2	Box Plot of Change from Baseline in Static Perimetry – Fellow Eye
Figure 14.2.2.2.1	Histograms of Static Perimetry – Study Eye
Figure 14.2.2.2.2	Histograms of Static Perimetry – Fellow Eye
Figure 14.2.2.3.1	Shift plots of Static Perimetry – Study Eye
Figure 14.2.2.3.2	Shift plots of Static Perimetry – Fellow Eye
Figure 14.2.2.4	Line Plots of Static Perimetry
OCT: Cystic cavity volume (mm [^] 3), Macular volume (mm [^] 3), Central segment (μm),	
Inner circle superior (μ m), Inner circle nasal (μ m), Inner circle inferior (μ m), Inner circle	

(μm), and Outer circle temporal (μm)	
Figure 14.2.3.1.1	Box Plot of Change from Baseline in OCT – Study Eye
Figure 14.2.3.1.2	Box Plot of Change from Baseline in OCT – Fellow Eye
Figure 14.2.3.2.1	Histograms of OCT – Study Eye
Figure 14.2.3.2.2	Histograms of OCT – Fellow Eye
Figure 14.2.3.3.1	Shift Plots of OCT – Study Eye
Figure 14.2.3.3.2	Shift Plots of OCT – Fellow Eye
Figure 14.2.3.4	Line Plots of Change from Baseline in OCT
Reading Speed: Maximum Reading Speed, Reading Acuity, Critical Print Size	
Figure 14.2.4.1	Box Plot of Reading Speed – Both Eyes
Figure 14.2.4.2	Histograms of Reading Speed – Both Eyes
Figure 14.2.4.3	Shift Plots of Reading Speed – Both Eyes
Figure 14.2.4.4	Line Plots of Reading Speed
Contrast Sensitivity	
Figure 14.2.5.1.1	Box Plot of Change from Baseline in Log Contrast Sensitivity – Study Eye
Figure 14.2.5.1.2	Box Plot of Change from Baseline in Log Contrast Sensitivity – Fellow Eye
Figure 14.2.5.2.1	Histograms of Log Contrast Sensitivity – Study Eye
Figure 14.2.5.2.2	Histograms of Log Contrast Sensitivity – Fellow Eye
Figure 14.2.5.3.1	Shift Plots of Log Contrast Sensitivity – Study Eye
Figure 14.2.5.3.2	Shift Plots of Log Contrast Sensitivity – Fellow Eye

temporal (μm), Outer circle superior (μm), Outer circle nasal (μm), Outer circle inferior

Figure 14.2.5.4	Line Plots of Contrast Sensitivity	
Full-field ERG: All continuous parameters		
Figure 14.2.6.1.1	Box Plot of Change from Baseline in Full-field Electroretinography – Study Eye	
Figure 14.2.6.1.2	Box Plot of Change from Baseline in Full-field Electroretinography – Fellow Eye	
Figure 14.2.6.2.1	Histograms of Full-field Electroretinography – Study Eye	
Figure 14.2.6.2.2	Histograms of Full-field Electroretinography – Fellow Eye	
Figure 14.2.6.3.1	Shift Plots of Full-field Electroretinography – Study Eye	
Figure 14.2.6.3.2	Shift Plots of Full-field Electroretinography – Fellow Eye	
Figure 14.2.6.4	Line Plots of Full-field Electroretinography
